CSP	Clinical Study Protocol
CSR	Clinical Study Report
CV	Coefficient of variation
CVID	Common variable immune deficiency
DBP	Diastolic blood pressure
eCRF	Electronic Case Report Form
FDA	Food and Drug Administration
FAS	Full analysis set
GMC	Geometric mean concentration
HBsAg	Hepatitis B surface antigen
HIV	Human immunodeficiency virus
HR	Heart rate
IP	Investigational Product
IWRS	Interactive web response system
LQ	Limit of quantification
MCAR	Missing completely at random
MedDRA	Medical Dictionary for Regulatory Activities
NK	Not known
NOCI	New onset of chronic illness
PD	Protocol deviation
PPS	Per Protocol Set
SAE	Serious adverse event
SAP	Statistical Analysis Plan
SBP	Systolic blood pressure
SD	Standard deviation or single dose

PAREXEL International
Statistical Analysis Plan

Abbreviation / Acronym	Definition / Expansion
SE	Standard error of the mean
SOC	System Organ Class
SPR	Seroprotection rate
SSA	Sub-study Analysis Set
SUSAR	Suspected unexpected serious adverse reactions
TEAE	Treatment-emergent adverse event
TLF	Tables, Listings and Figures
VBI	VBI Vaccines Inc
WHO-DD	World Health Organization - Drug Dictionary

PAREXEL International
Statistical Analysis Plan

STATISTICAL ANALYSIS PLAN

The Statistical Analysis Plan (SAP) details the statistical methodology to be used in analyzing study data and outlines the statistical programming specifications for the Tables, Listings and Figures (TLFs). It describes the variables and populations, anticipated data transformations and manipulations and other details of the analyses not provided in the Clinical Study Protocol (CSP).

The analyses described are based on CSP V4.0, dated 09May2018.

The SAP will be finalized prior to database unblinding and describes the statistical analysis as it is foreseen when the study is being planned. If circumstances should arise during the study rendering this analysis inappropriate, or if improved methods of analysis should arise, updates to the analyses may be made and this SAP will be amended. Any deviations from the SAP after database unblinding, reasons for such deviations and all alternative or additional statistical analyses that may be performed, will be described in the clinical study report (CSR).

1. STUDY OBJECTIVES

1.1 Primary Objective

To demonstrate the manufacturing equivalence, in terms of immunogenicity, of three independent consecutive lots of the Sci-B-Vac™ 4 weeks after the third vaccination. This objective will be met if the following condition is satisfied:

- The upper and lower bound of the two sided 95% CI of the geometric mean concentration (GMC) of anti-HBs ratios 4 weeks after the third vaccination, for all three pairwise comparisons (GMC of anti-HBs in group A/GMC of anti-HBs in group B, GMC of anti-HBs in group A/GMC of anti-HBs in group C, GMC of anti-HBs in group B/GMC of anti-HBs in group C) are within [0.67, 1.5].

1.2 Secondary Objectives

Immunogenicity

To demonstrate that the SPR 4 weeks after completion of the three-dose regimen of Sci-B-Vac™ is non-inferior to a three-dose regimen of Engerix-B®, i.e. the lower bound of the 95% two-sided confidence interval (CI) of the difference between the SPR Sci-B-Vac™ arm minus the SPR in the Engerix-B® arm, achieved 4 weeks after the third vaccination will be > -5 .

Safety

- To assess the safety and reactogenicity of Sci-B-Vac™ compared to Engerix-B®

PAREXEL International
Statistical Analysis Plan

1.3 Exploratory Objectives

The following are exploratory objectives:

- To assess the Geometric Mean Concentration (GMC) of anti-HBs in serum after 2 vaccinations, just prior to receiving the third vaccination, and 24 weeks after the third vaccination with Sci-B-Vac™ or Engerix-B®, on Study Days 168 and 336, respectively.
- To assess the seroprotection rate after 2 vaccinations, just prior to receiving the third vaccination, and 24 weeks after the third vaccination with Sci-B-Vac™ or Engerix-B®, on Study Days 168 and 336, respectively. Seroprotection is defined as anti-HBs levels $\geq 10\text{mIU/mL}$ in serum. Seroprotection Rate (SPR) is the percentage (%) of subjects achieving seroprotection.
- To assess the Proportion of subjects achieving anti-HBs levels $\geq 100\text{mIU/mL}$ in serum, as a measure of an especially robust immune response, on Study Days 168 and 196, just prior to and 4 weeks after the third vaccination with Sci-B-Vac™ or Engerix-B®, and on Study Day 336.
- To assess the rate of non-response on Study Day 196, 4 weeks after the third vaccination with Sci-B-Vac™ or Engerix-B®. Rate of non-response is defined as the proportion of subjects not attaining anti-HBs levels $\geq 10\text{mIU/mL}$ in serum.
- To assess SPR, GMC and rate of non-response in sub-groups of interest (e.g. BMI > 30), 4 weeks after receiving the third vaccination with Sci-B-Vac™ or Engerix-B®.
- To determine whether the SPR after 2 vaccinations with Sci-B-Vac™, evaluated 20 weeks after the second vaccination (just prior to receiving the third vaccination), is non-inferior to the SPR 4 weeks after receiving the third vaccination with Engerix-B®.

[figure not shown]
2. STUDY DESIGN

This is a double-blind 4-arm randomized study. Subjects age 18-45 years will be randomly assigned to one of 3 lots of Sci-B-Vac™ or to Engerix-B® with a ratio 1:1:1:1 using a web-based randomization system to be immunized against Hepatitis B virus (HBV), according to a three-dose immunization schedule and followed for 24 weeks after the third immunization. The total study duration for each subject (assuming a screening period of 28 days or 4 weeks) is 364 days or 52 weeks.

The scheme of the study design is as Figure 1. For further details please refer to [section 3.1 of the Protocol](#).

PAREXEL International Statistical Analysis Plan

Figure 1: Schematic of Study Design

3. STUDY POPULATION

Per protocol, the study population will consist of approximately 3200 adult subjects (18-45 years) in at least 30 study centers in the E.U., Canada and the U.S. of all races and ethnic groups meeting all the inclusion criteria and none of the exclusion criteria. The final study population consisted of approximately 2800 adult subjects after an early closure to enrollment (see [Section 4](#)).

Inclusion criteria

Subjects must meet all the following criteria:

1. Any gender.
2. Age 18-45 years.
3. Healthy, as determined by a physical examination and values of laboratory tests.
4. If female: a) either not of childbearing potential, defined as postmenopausal for at least 1 year or surgically sterile (bilateral tubal ligation, bilateral oophorectomy or hysterectomy), OR b) is of childbearing potential and must agree to use an adequate birth control method during the screening period and until the end of her participation in the study (effective birth control includes: 1) hormonal

PAREXEL International Statistical Analysis Plan

(implant, oral, vaginal, transdermal) contraceptives; 2) diaphragm with spermicide, condom (with or without spermicide); 3) intra-uterine devices; and 4) vasectomy of male partner; 5) abstinence from penile-vaginal intercourse (if the preferred and usual lifestyle of the subject)).

5. Able and willing to give informed consent.

Main Exclusion criteria

Main exclusion criteria are listed below, for the complete list of exclusion criteria please refer to [section 4.1.2 of the Protocol](#). Participants meeting any of the exclusion criteria will be excluded.

1. Previous vaccination with any HBV vaccine (licensed or experimental).
2. Treatment by immunosuppressant within 30 days of enrollment including but not limited to corticosteroids at a dose that is higher than an oral or injected physiological dose, or > 20 mg /day prednisolone equivalent (Inhaled and topical steroids are allowed).
3. History of immunological function impairment, including but not limited to:
 - a) autoimmune diseases (e.g., multiple sclerosis, type 1 diabetes, myasthenia gravis, Crohn disease and other inflammatory bowel diseases, celiac disease, systemic lupus erythematosus, scleroderma, including diffuse systemic form and CREST syndrome, systemic sclerosis, dermatomyositis polymyositis, rheumatoid arthritis, juvenile idiopathic arthritis, autoimmune thyroiditis -including Hashimoto thyroiditis, Grave's or Basedow's disease, immune thrombocytopenic purpura, autoimmune hemolytic anemia, autoimmune hepatitis, psoriasis, vitiligo, vasculitis, Guillain-Barré syndrome, Addison's disease, Bell's Palsy and Alopecia Areata);
 - b) secondary immunodeficiency disorders (e.g. Acquired Immunodeficiency Syndrome caused by Human Immunodeficiency Virus infection (HIV/AIDS), solid organ transplant, splenectomy);
 - c) primary immunodeficiency disorders (e.g. common variable immune deficiency (CVID), Defective phagocytic cell function and neutropenia syndromes, complement deficiency).
4. Pregnancy or breastfeeding.
5. Immunization with attenuated vaccines (e.g. MMR) within 4 weeks prior to enrollment.
6. Immunization with inactivated vaccines (e.g. influenza) within 2 weeks prior to enrolment.

4. STATISTICAL BASIS FOR SAMPLE SIZE

The sample size for this study is driven by the lot-to-lot consistency requirement. A total of 800 subjects in each of the three Sci-B-Vac™ lots will provide at least 90% power to ensure that the 95% confidence interval for each pairwise difference (GMC of anti-HBs in group A/GMC of anti-HBs in group B, GMC of anti-HBs in group A/ GMC of anti-HBs in group C, GMC of anti-HBs in group B/ GMC of anti-HBs

PAREXEL International Statistical Analysis Plan

in group C) in normalized log₁₀ (GMC) will have a lower bound that is >-0.176 and an upper bound that is <0.176 if the true standard deviation is ≤ 0.9 ; this corresponds to the true GMC ratio falling between $2/3$ and $3/2$. With an active comparator arm of Engerix-B[®] of equal size ($n=800$), the total sample size of the study is 3,200.

If lot-to-lot consistency is demonstrated, all three Sci-B-Vac[™] lots will be pooled together to test that the Seroprotection Rate (SPR) four weeks after completion of the three-dose regimen of Sci-B-Vac[™] is non-inferior to a three-dose regimen of Engerix-B[®]. Assuming 10% of the subjects are non-evaluable (i.e., 2880 are evaluable, with 2160 randomized to Sci-B-Vac[™] and 720 to Engerix-B[®]), a two-sided 5% significance level and a non-inferiority margin of -5% , the non-inferiority test will have $> 90\%$ power. The following table provides the estimated power under different assumptions of the SPR four weeks after completion of the three-dose regimens.

Response in Engerix-B [®] (N=720)	Response in Sci-B-Vac [™] (N=2160)	Power
80%	85%	99%
85%	85%	92%
90%	95%	99%

In October 2018, enrollment was closed early for non-safety-related reasons after 2838 were randomized to the study. With approximately 700 subjects in each of the three Sci-B-Vac[™] lots and 700 subjects in comparator arm of Engerix-B[®], the sample size will provide $> 80\%$ power to evaluate both the primary objective of lot to lot consistency of the three Sci-B-Vac lots, and the secondary objective of non-inferiority of Sci-B-Vac[™] vs Engerix-B[®].

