6.3.13.1 Primary Hypothesis

The lot-to-lot equivalence, in terms of immunogenicity, of three independent consecutive lots of the Sci-B-Vac™ will be demonstrated if the following condition is satisfied:

The upper and lower bound of the two sided 95% CI of the geometric mean concentration (GMC) of anti-HBsAg antibody ratios 4 weeks after the third injection for all three pairwise comparisons (GMC(group A)/GMC(group B), GMC(group A)/GMC(group C), GMC(group B)/GMC(group C)) are within [0.67, 1.5]

The analysis will use a two-sided 5% significance level. PPS1 and PPS2 will be used to test the primary hypothesis.

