6.3.13.2 Statistical Methods for Primary Immunogenicity Analyses

Geometric mean concentration (GMC) of anti-HBsAg antibody ratios 4 weeks after the third injection

All statistical analyses will be performed on the logarithmically (base 10) transformed values.

Adjusted estimates of GMCs and their associated 95% CIs will each be determined using an analysis of covariance (ANCOVA) model with a factor for vaccine lot group, and a covariate for the log transformed pre-vaccination (baseline) titer. Data from all centers will be pooled. For each vaccine lot, antibody GMCs, associated standard errors, two-sided 95% CIs and median, minimum, and maximum titer values will be determined and presented by lot group. The median, minimum, and maximum values will be reported on the actual titer values, rather than the log scale. The ratio in GMCs between each vaccine lot group (GMC(group A)/GMC(group B), GMC(group A)/GMC(group C), GMC(group B)/GMC(group C)), and their associated two-sided 95% CIs will also be presented.

PAREXEL International

Statistical Analysis Plan

Sensitivity analyses using the same modeling approach outlined above will be conducted using the FAS. These analyses will be reported both with and without patients in the FAS who are seropositive at baseline.

If this condition is satisfied with either PPS1 or PPS2, then manufacturing equivalence (lot-to-lot consistency) will be demonstrated.

Sample SAS code for assessment of lot-to-lot equivalence:

- Sample SAS code for ANCOVA model:

```
PROC MIXED;  
CLASS treatment;  
MODEL log (var) = treatment log (baseline of var);  
LSMEANS treatment / DIFF CL ALPHA=0.05;  
ODS OUTPUT LSMEANS=ls_means Diffs=diff;  
QUIT;
```

where var represent the anti-HBs titer and treatment represents vaccine lot group.

6.3.13.3 *Secondary Objective Analyses*

If lot-to-lot consistency is demonstrated, then the data from the three lots will be combined to address the secondary immunogenicity non inferiority-hypothesis. It is to demonstrate that the SPR 4 weeks after completion of the three-dose regimen of Sci-B-Vac™ is non-inferior to the SPR 4 weeks after completion of a three-dose regimen of Engerix-B®. Seroprotection is defined as anti-HBs levels ≥ 10 mIU/mL in serum. Seroprotection rate (SPR) is the percentage (%) of subjects achieving seroprotection.

Seroprotection rate (SPR) 4 weeks after the third injection

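### The power above 80% re-issued for the primary objective after early closure does not hold at SD 0.9 with 10% non-evaluable; it is about 71–75%

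*SAP*

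**What the plan says.** Section 4 of the SAP first sizes the trial at 800 per lot. It gives at least 90% power that the confidence interval for each pairwise difference in log10 GMC lies within ±0.176, for a true SD of at most 0.9. The non-inferiority paragraph then adds an attrition rate: "Assuming 10% of the subjects are non-evaluable". That leaves 2880 of 3200 subjects, of whom 2160 are on Sci-B-Vac.

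The section ends with the early closure in October 2018, after 2838 subjects were randomised. It states that about 700 per arm gives more than 80% "power to evaluate both the primary objective of lot to lot consistency of the three Sci-B-Vac lots, and the secondary objective of non-inferiority". It names no SD, true lot difference or evaluable number for this figure.

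Three other places define what that power must cover:

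- Section 1.1 requires the limits to be met "for all three pairwise comparisons".
- Section 6.3.13.1 fixes the analysis sets: "PPS1 and PPS2 will be used to test the primary hypothesis".
- Section 6.3.13.2 gives the decision rule: "If this condition is satisfied with either PPS1 or PPS2, then manufacturing equivalence (lot-to-lot consistency) will be demonstrated".

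Section 6.3.13.3 makes the non-inferiority test depend on this result: "If lot-to-lot consistency is demonstrated, then the data from the three lots will be combined".

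**The concern.** The planned power is worded for one pair at a time, whereas the post-closure power is claimed for the primary objective as a whole. Passing all three pairs together is harder than passing any one of them. The objective is also tested in per-protocol sets, so the number analysed is smaller than the number randomised. If the post-closure figure allows for neither point, it is too high.

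This is the one power figure re-issued after enrolment stopped about 11% short (2838/3200 = 0.887). A reader faced with a failed lot-consistency result would use it to judge how likely a chance failure was. Because non-inferiority is tested only after lot consistency is shown, the chance of meeting both objectives cannot exceed the chance of meeting the first.

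**Working it through.** **Inputs**

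- Bounds ±0.176 on the log10 scale, SD 0.9: section 4.
- Two-sided 95% CI for each pair, all three pairs required: sections 1.1 and 6.3.13.1.
- Randomised per lot: 2838/4 ≈ 709, or the rounded 700 that section 4 uses.
- Non-evaluable 10%: section 4. Evaluable per lot: 0.9 × 709 ≈ 638, or 0.9 × 700 = 630.
- True lot difference: not stated. Taken as zero, the most favourable case.
- Size of PPS2 relative to PPS1: not stated. Assumed 90%, 95% or 98%.

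**Formulas**

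One pair: power = 2Φ(0.176/SE − 1.96) − 1, with SE = 0.9·√(2/n).

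All three pairs, one set: success when the range (largest minus smallest) of the three lot means plus the CI half-width, 1.96·SE, is below 0.176. The probability was obtained by simulation (2 million replicates, pooled variance, t quantiles).

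**The planned figure first.** At n = 800, SE = 0.9 × 0.05 = 0.045, 0.176/0.045 = 3.911, and power = 2Φ(1.951) − 1 = 94.9% for one pair. The stated 90% or more per pair is confirmed. For all three pairs it is 87.5%.

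**After closure, worked at n = 638.** SE = 0.9·√(2/638) = 0.0504.

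- One pair: 0.176/0.0504 = 3.493, so power = 2Φ(1.533) − 1 = 87.5%.
- All three: the half-width is 1.96 × 0.0504 = 0.0988, so the range must stay below 0.176 − 0.0988 = 0.0772. The standard error of one lot mean is 0.9/√638 = 0.0356, so the limit is 2.17 standard errors. The range of three independent means stays below that with probability 72.4%.

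| Evaluable per lot | One pair | All three, one set | All three, PPS1 or PPS2 |
|---|---|---|---|
| 709 (no loss) | 91.5% | 80.3% | 81.7–82.4% |
| 700 (no loss) | 91.1% | 79.4% | 81.0–81.6% |
| 638 (10% loss) | 87.5% | 72.4% | 74.3–75.1% |
| 630 (10% loss) | 86.9% | 71.3% | 73.3–74.1% |

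The last column comes from the same simulation with PPS2 nested in PPS1; its range reflects the assumed 90–98%.

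**What would give 80% for all three pairs**

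- At SD 0.9: about 707 evaluable per lot in one set, or about 684–691 under the either-set rule.
- After 10% loss: an SD of about 0.85 in one set (80.0% at 630, 80.9% at 638), or about 0.86 under the either-set rule (80.0–80.7% at 630, 80.8–81.5% at 638).

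**Non-identical lots.** At 630 per lot in one set, power falls to 68.6% if the true means span 0.02 log10 and to 55.7% if they span 0.05.

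**Non-inferiority alone.** Exact enumeration of the Miettinen–Nurminen test at 85% against 85% gives 92.5% for 2160 against 720, matching the stated 92%. It gives 88.9% for 1890 against 630 and 89.3% for 1915 against 638. This half of the claim stands.

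**The case against.** The best defence is that the sentence merely puts 700 in place of 800 on the same basis as the planned calculation. Read per pair, power is 91.1% at 700 and still 86.9% at 630. Read for all three pairs with no attrition, the either-set rule gives 81.0–81.6% at 700. The 10% loss is written only in the non-inferiority paragraph, and 0.9 is a ceiling on the SD rather than an estimate of it. Enrolment had also closed, so nothing in the analysis turns on the figure.

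Part of this stands. The figure is not arithmetically impossible, and carrying the 10% over to the primary objective is an inference. It is a sound one: the rate is applied to all 3200 subjects, and 2160 is exactly 3 × 720 subjects from the same lots. PPS1 further requires three doses, evaluable samples, baseline seronegativity and no excluding deviation, so zero loss is not realistic. The per-pair reading does not fit a sentence that names the primary objective. The SD of 0.9 is the only one the section gives, and the planned power is promised up to it. The baseline covariate in the ANCOVA should recover little, since per-protocol subjects are seronegative at baseline.

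**Conclusion.** The concern holds. At SD 0.9, identical lots and 10% non-evaluable, power for the primary objective is about 71–72% in one per-protocol set and about 73–75% under the either-set rule. The chance of missing the objective with identical lots is therefore about 25–29%, not under 20%. The either-set range rests on the assumed overlap of PPS1 and PPS2, and the whole result rests on the SD being at its stated limit; at about 0.85–0.86 the 80% is recovered. The per-pair statement at 800 and the stand-alone non-inferiority power are not in question. The defect lies in a reported power figure and does not affect the validity of the analysis.

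**What to change.** Restate only the post-closure sentence in section 4, with its conditions. For example:

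> With about 709 randomised per lot and 10% non-evaluable (about 638), SD 0.9 and no true lot difference, power is about 87% for each pair and about 72% for all three pairs in one per-protocol set (about 74–75% if either PPS1 or PPS2 may satisfy the condition, assuming PPS2 is 90–98% of PPS1). Power for all three pairs reaches 80% if the SD is about 0.85 or less. Non-inferiority power taken alone is about 89% at 85%/85% and is conditional on lot consistency being shown.

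The parenthesis on the either-set rule may be dropped if the team prefers not to write an assumed PPS2 size into the SAP. The planned 90% sentence needs no correction, though the all-three-pairs figure at 800 (about 87.5%) could be added beside it. The cost is one sentence of wording and a less favourable stated power for the primary objective.

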5. RANDOMIZATION

A statistician who is not involved in the clinical aspects of the study will generate a permuted blocked randomization list for each site. Randomization will be via a web-based IWRS, stratified by study center. The site pharmacy and/or unblinded study center staff will receive a notification of the randomization, which should be filed in a locked area/ computer folder not accessed by blinded study center staff.

5.1 Definition of Vaccination/Randomization Errors

The list below provides some examples of potential errors that may occur during vaccination:

PAREXEL International
Statistical Analysis Plan

- Subjects vaccinated with a Sci-B-Vac™ lot different from the one assigned Sci-B-Vac™ lot at randomization.
- Subjects vaccinated with the correct Sci-B-Vac™ lot but containing a lower volume.
- Subjects vaccinated with a vaccine different from the one assigned at randomization.

Please see [section 6](#) of this document for a complete guidance on how vaccination/randomization errors are handled in the statistical analysis.

6. STATISTICAL ANALYSIS CONVENTIONS

6.1 Analysis Variables

Baseline characteristics, medical history, vaccination, immunogenicity (measurement of anti-HBs), concomitant medication, adverse events (AEs) and other safety assessments will be assessed according to the schedule of events listed as following:

	Screening Visit	V1	Safety Follow-up Phone Call	V2	Safety Follow-up Phone Call	Safety Follow-up Phone Call	V3	Safety Follow-up Phone Call	V4 (I)	V5 End of Study Visit
Timelines (days)	-28	0		28			168		196	336(a)
Range (days)	-28 to 0		V1 + 5-9	-3/+7	V2 + 5-9	V2 +21-35	+/-7	V3 + 5-9	+/-7	+/-14
Screening										
Informed Consent	X									
Physical Exam (b)	X	X		X			X		X	X
Medical History	X									
Height and weight	X									
Medications	X									
HBV serology	X									
HIV and HCV serology	X									
Urine Pregnancy test	X	X		X			X			
Serum chemistry, hematology, HbA1C	X									
Urinalysis	X									
Inclusion & Exclusion Criteria	X									
Confirmation of enrollment	X	X								
Vaccination		X		X			X			
Immunogenicity		X (c)					X (c)		X	X
Safety Assessments										
Vital signs	X	X (d)		X (d)			X (d)		X	
Subject instructed to complete diary		X	X	X	X		X	X		
Local & Systemic Reactions		X	X(e)	X	X(e)	X(e)	X	X(e)		

PAREXEL International Statistical Analysis Plan

Unsolicited Non Serious AEs		X	X(g)	X(g)	X(g)	X(g)	X(f)	X(g)	X(g)	X(f)
Concomitant Medications	X	X	X	X	X	X	X	X	X	X
Serious Adverse Events, Medically significant event and NOCI (h)	Continuous									
Sub-Study (select sites)			A1*		A2*			A3*		
Serum chemistry, hematology		X (c)	X(j)		X(j)			X(j)		
	
(a) Or earlier in case of withdrawal (reason for withdrawal to be documented in eCRF)
 
(b) Full physicals to be done at screening or pre-vaccination at Day 0. History-directed physicals can be completed at subsequent visits.
 
(c) Blood sample will be taken before vaccination
 
(d) Vital signs will be recorded before and 30 minutes after each vaccination.
 
(e) Subjects will be instructed to record solicited and unsolicited AEs. There will be a telephone call 7 days (+/-2 days) after each vaccination, and 28 days (+/- 7 days) after the second vaccination to inquire about AEs. If there is a reaction the subject may be asked to come for a supplemental visit (not represented in this table) to assess severity at the discretion of the investigator. Follow-up until resolution.
 
(f) Only AEs requiring medical attention
 
(g) All AEs
 
(h) NOCI = new onset of chronic illness
 
(i) Visit 4 should be scheduled at least 3 weeks after Visit 3
 
(j) Blood sample collected 7 days (-3/+7 days) after vaccination
 
*Additional visits (A1, A2 and A3) required for study subjects at select sites participating in the clinical laboratory sub-study.
									

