6.2.5.2 Per Protocol Set 2 (PPS2)

All subjects in PPS1, but excluding those who attended study visits outside of the following windows:

- V3/Day 168 (+/- 28 days)
- V4/Day 196 (-7/+14 days)

PPS2 will be used for the primary, secondary, and exploratory endpoints.

In case of vaccination error, subjects in PPS1 and/or PPS2 will be analyzed “as randomized” and the subject who received the wrong vaccination will be excluded from PPS1 and/or PPS2. If a subject receives a vaccine from the wrong kit number, but the same as the one the subject was randomized to, the subject will not be removed from PPS1 and/or PPS2.

If a subject is unblinded during the study, except for suspected unexpected serious adverse reaction (SUSAR), he/she may be excluded from PPS1 and/or PPS2 based on sponsor’s decision with respect to any potential bias that may be introduced in the analysis of the primary and key secondary immunogenicity analyses.

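### No Day 336 sampling window in PPS2, so early-withdrawal Visit 5 samples can be analysed as exploratory Day 336 results

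*SAP*

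**What the plan says.** - **Schedule, SAP 6.1.** Day 336 is the "V5 End of Study Visit", with a range of ±14 days and an immunogenicity sample. Footnote (a) on that day reads "Or earlier in case of withdrawal".
- **Visit mapping, SAP 6.3.4, Table 1.** Nominal Visit 5 becomes analysis visit Day 336, target study day 337. There is no window and no row for early termination. Unscheduled assessments stay out of summaries. Where several assessments fall within one analysis visit, the one nearest the target day is used.
- **Per protocol sets, SAP 6.2.5.** PPS1 requires all three doses and evaluable samples at baseline and at the relevant time point, with no day range. PPS2 is defined as "All subjects in PPS1, but excluding those who attended study visits outside of the following windows". The list that follows has two entries: V3 at Day 168 ±28 days and V4 at Day 196 −7/+14 days. Visit 5 is not on it.
- **Use of PPS2.** SAP 6.2.5.2 states "PPS2 will be used for the primary, secondary, and exploratory endpoints", and 6.3.13.4 makes PPS2 the default for exploratory immunogenicity. Section 1.3 places GMC and SPR at Day 336, described as 24 weeks after dose 3, and the proportion with anti-HBs ≥100 mIU/mL at Day 336 among other days. Section 6.3.13 adds a PPS2 bar plot of SPR that includes Day 336.

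**The concern.** Three post-vaccination time points carry immunogenicity samples: Days 168, 196 and 336. The SAP sets analysis windows for the first two and none for the third, which is the one whose visit may be brought forward under the schedule. Because footnote (a) makes the early sample a planned Visit 5 sample, the rule that keeps unscheduled assessments out of summaries does not catch it.

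Day 336 results will be read as persistence of the response. A sample taken a few weeks after dose 3 does not measure that, whatever its visit label. If titers fall after Day 196, such samples push the Day 336 GMC, SPR and ≥100 mIU/mL proportion upward.

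**Working it through.** The SAP states no expected value, sample size or power for Day 336, so there is no plan figure to reproduce. The check has two parts.

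**1. Do the written rules stop an early sample?** Take a subject with doses on Days 0, 28 and 168, V4 on Day 196, and withdrawal with a Visit 5 sample on Day 220 (an illustrative day).

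- Time since dose 3: 220 − 168 = 52 days, about 7 weeks. Intended: 336 − 168 = 168 days, or 24 weeks.
- PPS1 dose rule: met.
- PPS2 windows: V3 and V4 both within range, and Visit 5 is not tested.
- Table 1: nominal Visit 5 is labelled Day 336.
- Nearest-to-target rule: it chooses among several assessments within one visit, so it cannot remove a single one.
- Missing-data rule (6.3.5): it covers absent values, not early values carrying a Day 336 label.

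No explicit rule removes the sample. Subjects who withdrew before dose 3 are already outside PPS2.

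**2. How large could the effect be?** Let f be the share of an arm's Day 336 values that are early samples, and W the ratio of an early titer to the titer the same subject would have had at Day 336. Neither is in the SAP, so both are assumed. With the GMC formula in 6.1.1, the mean log10 titer rises by f × log10(W), so the GMC is multiplied by W^f. This ignores the baseline covariate and assumes that withdrawers would otherwise resemble the rest of the arm.

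| | f = 1% | f = 5% | f = 10% |
|---|---|---|---|
| W = 2 | 1.007 | 1.035 | 1.072 |
| W = 5 | 1.016 | 1.084 | 1.175 |

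For SPR, the inflation is f × (SPR at the early sample − SPR at Day 336). With an assumed 5-point fall it is 0.05, 0.25 and 0.5 points at f = 1%, 5% and 10%. With a 10-point fall it is 0.1, 0.5 and 1.0 points. The same formula applies to the ≥100 mIU/mL proportion.

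For the between-arm GMC ratio:

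- Equal f and equal W: the factors cancel and there is no shift.
- Early shares of 5% and 2%, W = 5 in both arms: 5^(0.05 − 0.02) = 5^0.03 = 1.049.
- Share of 5% in both arms, W = 5 in one and 2 in the other: (5/2)^0.05 = 1.047.

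**Scale.** Section 4 gives a log10 SD of at most 0.9 and about 700 subjects per arm after early closure. Borrowing these for Day 336 (an assumption, since PPS2 will be smaller and the Day 336 SD is not stated):

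- One arm's GMC: 1.96 × 0.9/√700 = 0.0667, so the 95% CI factor is 10^0.0667 = 1.166.
- Pooled lots (2100) against comparator (700): 1.96 × 0.9 × √(1/2100 + 1/700) = 0.0770, a factor of 1.194.

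The two illustrated ratio shifts lie well inside the second interval.

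**The case against.** The strongest reply is that PPS1, and so PPS2, already requires an evaluable sample at the relevant time point. For this endpoint that is 24 weeks after dose 3, so a sample at about 7 weeks fails on a literal reading. Visit schedule is also a protocol-deviation category (6.3.7.1), and PPS1 can drop subjects whose deviations are judged to affect immunogenicity results. Actual sampling times are listed and plotted (6.3.13), so early samples would be visible. Finally, Table 1 is introduced for laboratory, vital sign and physical examination data and does not name serology.

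Part of this stands. Inclusion is permitted by omission and is not ordered, so it would be wrong to infer that early samples will certainly be analysed as Day 336. But the time-point clause has no day range, and footnote (a) makes the early visit an allowed one, so it need not count as a deviation. Exclusion for a major deviation also acts on the subject and could cost a valid Day 196 value. If Table 1 does not cover serology, the SAP has no visit-assignment rule for anti-HBs at all, which leaves the gap wider.

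A reader might also infer that the FAS is affected, with withdrawals before dose 3 labelled Day 336. The documents do not clearly support that. The FAS sensitivity analyses are spelled out for lot consistency and for Day 196 SPR, and exploratory endpoints default to PPS2. Such subjects would not have less-waned post-dose-3 titers in any case.

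**Conclusion.** The gap is real but minor. As written, the rules allow early-withdrawal samples from three-dose subjects into the PPS2 Day 336 summaries, and whether they enter is left to whoever applies the text.

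Upward bias is conditional on waning after Day 196. A subject who withdraws between V3 and V4 may be sampled before the peak, so the direction is not certain for every sample. The size cannot be known from the SAP. It is probably small unless many subjects withdraw after dose 3, and the figures above rest wholly on assumed shares and falls.

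Two stronger conclusions are not supported. One is that the vaccine comparison at Day 336 is biased: that needs a difference between arms in early share or in waning, and nothing in the SAP indicates one. The other is that the trial's main conclusions are at risk: the primary lot comparison and the secondary non-inferiority test use Day 196, and the Day 336 endpoints are exploratory with no success criterion.

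**What to change.** In SAP 6.2.5.2, for Day 336 endpoints only, require the Visit 5 sample to fall within a stated window. The schedule's own ±14 days (Days 322 to 350) is one choice; a wider stated tolerance, as already allowed for V3, is another. State that early-withdrawal samples outside the window are listed but not summarised as Day 336. Those subjects then count as missing at Day 336 under the complete-case rule in 6.3.5.

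Apply the rule to the time point and not to the subject, so that valid Day 168 and Day 196 data stay in PPS2. If a FAS analysis of Day 336 is actually run, use the same window there.

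The cost is one line of text and one visit-window flag, and a few samples leave the Day 336 summaries. The rule should be in place before unblinding, when the SAP is to be final.
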